6.11.8.2.1. Analyses of Characteristics of ADA Immune Response

The analyses of ADA effects will be conducted on all evaluable patients within the defined Safety Population for Blinded Treatment Dosing Period (Period 2), and Combined Blinded Treatment Dosing and Extended Treatment Periods (Combined Periods 2 and 3).

Baseline definition for immunogenicity analyses for the Combined Treatment Period is the same as [Table RHCH.6.9](#).

The overall frequency and percentage (incidence) of patients will be summarized for the TE-ADA status groups and the time-varying TE-ADA status groups. Scheduled visits, unscheduled visits, and repeat measurements will be included.

In addition, the overall frequency and percentage (incidence) of patients will be summarized for the patients who are baseline ADA positive by TE-ADA status groups. For those patients who are TE-ADA positive, a summary of titer values and the proportion of patients who are NAb positive will also be provided.

The time to the development of TE-ADAs (TE-ADA positive, low titer, moderate titer, high titer, and NAb positive) will be calculated as follows:

Time to development of TE-ADAs/NAb (in weeks) = (Date of development of TE-ADAs/NAb – Date of first injection of study treatment + 1) / 7.

If a patient has not developed TE-ADAs/NAbs, they will be censored at the date of the last immunogenicity assessment.

Descriptive statistics, including 25th percentile, 50th percentile (median), 75th percentile, and corresponding 95% CIs as well as proportion of TE-ADA/NAb positive by endpoint summarized by treatment group, will also be provided if sufficient data is present. A Kaplan-Meier plot of the time to development of treatment-emergent ADA/NAb will be presented by treatment group, also if sufficient data is present.

For each TE-ADA status dichotomous variable (as defined in [Table RHCH.6.10](#)), summaries will be provided of the total postbaseline time in the greater-TE-ADA status for patients who were at some point postbaseline in the greater-TE-ADA status group. Postbaseline time in greater-TE-ADA status for each patient will be aggregated.

A by-patient listing to include treatment, visit date, visit, ADA result, TE-ADA result, NAb result, ADA titer value, ixekizumab concentration, ADA and NAb inconclusive results will also be provided, for patients with any one sample of ADA (or NAb) positive or inconclusive.

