8.1. Discontinuation from Study Treatment

The reason for and date of discontinuation from study treatment (investigational product) and reason for and date of discontinuation from study participation will be collected for all randomized patients.

8.1.1. *Permanent Discontinuation from Study Treatment*

For any patient permanently discontinuing from study treatment, the investigational product will be withheld, and the patient will complete the ETV and the Post-treatment Follow-up Period (Period 4), as shown in the Schedule of Activities (Section 2).

The following criteria must be followed for discontinuation from study treatment.

- **Subject Decision**
 - the patient or the patient's designee, for example, parents or legal guardian requests to discontinue investigational product.
- **Discontinuation due to a hepatic event or liver test abnormality.** Patients who are discontinued from investigational product due to a hepatic event or liver test abnormality should have additional hepatic safety data collected via electronic data entry.

Discontinuation of the investigational product for abnormal liver tests should be considered by the investigator when a patient meets one of the following conditions, after consultation with the Lilly designated medical monitor:

- alanine aminotransferase (ALT) or aspartate aminotransferase (AST) >8X upper limit of normal (ULN)
 - ALT or AST >5X ULN for more than 2 weeks
 - ALT or AST >3X ULN and total bilirubin (TBL) level >2xULN or international normalized ratio (INR) >1.5
 - ALT or AST >3X ULN with the appearance of fatigue, nausea, vomiting, right upper-quadrant pain or tenderness, fever, rash, and/or eosinophilia (>5%)
 - alkaline phosphatase (ALP) >3X ULN
 - ALP >2.5X ULN and TBL >2X ULN
 - ALP >2.5X ULN with the appearance of fatigue, nausea, vomiting, right upper quadrant pain or tenderness, fever, rash, and/or eosinophilia (>5%)
- Other laboratory tests

- Neutrophil (segmented) counts (see safety monitoring for neutropenia in Section 9.4.10.2):
 - <500 cells/ μL ($<0.50 \times 10^3/\mu\text{L}$ or <0.50 GI/L)
 - ≥ 500 and <1000 cells/ μL ($\geq 0.50 \times 10^3/\mu\text{L}$ and $<1.00 \times 10^3/\mu\text{L}$ or ≥ 0.50 GI/L and <1.00 GI/L) (based on 2 test results; the second test performed within 1 week from knowledge of the initial result)

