6.1.1. General Considerations for Analyses during the Blinded Treatment Dosing Period (Period 2)

Comparisons between ixekizumab regimen 80 mg Q4W and placebo will be performed for all analyses in Period 2.

Period 2 starts at the first injection of study treatment at Week 0 (Visit 2) and ends prior to the first injection of study treatment at Week 16 (Visit 8) or the ETV (between Weeks 0 and 16). If a patient has Visit 8 but does not receive injection at Week 16 (Visit 8), the last recorded time for Visit 8 is used as the end time for Period 2.

Baseline will be defined as the last available value before the first injection for efficacy, health outcome, and safety analyses. In most cases, this will be the measure recorded at Week 0 (Visit 2). For efficacy measures, if the patient does not take any injection, the last available value on or prior to randomization date will be used. Change from baseline will be calculated as the visit value of interest minus the baseline value. For safety analyses using a baseline period, the baseline period is defined as the time from Visit 1 to the date/time of the first injection.

The randomization to treatment groups is stratified by baseline CRP status (nonelevated versus elevated) and TNF inhibitors experience (experienced or naïve) as described in Section 5.2. Unless otherwise specified, the statistical analysis models will adjust for baseline CRP status, and prior TNF inhibitors experience(if applicable).

The primary analysis method for treatment comparisons of categorical efficacy and health outcomes variables at specific time points will be made using a logistic regression analysis with treatment, baseline CRP status, and TNF inhibitors experience (if applicable) in the model. The proportions, odds ratio and 95% confidence intervals (CIs) will be reported; treatment difference and 95% CIs will also be reported. Secondary analysis will be conducted using a Fisher's exact test. In the case when logistic regression model does not produce statistical results due to sparse data, Fisher's exact test will be used.

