6.11.8.1.3. Definitions for Clinical Interpretation of Assay Results

- **Baseline:** For immunogenicity analyses during Period 2, baseline is the last nonmissing observation on, or prior to, the date of the first injection of study treatment (Week 0). Unless otherwise specified, the baseline for Period 3 is defined as the last non-missing observation on, or prior to, the date of first injection of ixekizumab. For patients originally randomized to ixekizumab during Period 2, baseline is the last non-missing observation on, or prior to, the date of the first injection of study treatment for Period 2 (Week 0). For patients who are not originally randomized to ixekizumab in Period 2, baseline is the last non-missing observation on, or prior to, the date of the first injection of ixekizumab. See [Table RHCH.6.9](#) for further details.

Table RHCH.6.9. Baseline Definition for Immunogenicity Analyses for Extended Treatment Period

Treatment Assignment for Blinded Treatment Dosing Period (Period 2)	Treatment Assignment for Extended Treatment Period (Period 3)	Baseline for Extended Treatment Period Analysis ^a
Ixekizumab	Ixekizumab	Week 0
Placebo	Ixekizumab	Week 16

^a Last non-missing observation on, or prior to, the date of the first injection of study treatment at the defined week.

- **Baseline ADA positive (preexisting antibody) patient:** ADA detected in a sample collected at baseline.
- **Baseline ADA-negative patient:** ADA is not detected in a sample collected at baseline.
- **TE-ADA positive patient:** a) a patient with a ≥ 4 -fold increase over a positive baseline antibody titer (Tier 3); or b) for a negative baseline titer, a patient with an increase from the baseline to a level of $\geq 1:10$.
- **TE-ADA inconclusive patient:** A patient without a TE-ADA positive sample and with at least one sample for which drug levels may interfere with the ADA assay.
- **TE-ADA negative patient:** A patient who is evaluable for TE-ADA and is not either TE-ADA positive or TE-ADA inconclusive.
- **Incidence of TE-ADA:** Patients with TE-ADA as a proportion of the evaluable patient population during the treatment period. This excludes unevaluable patients.

All ADA positive samples will be evaluated for NAb. Definitions for NAb patient status will be defined as follows:

- **NAb-positive patient:** A patient where a NAb positive result is detected for ≥ 1 TE-ADA positive samples.

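### For Combined Periods 2 and 3, the time-to-TE-ADA/NAb clock starts at the first study-treatment injection (Week 0), while the placebo/ixekizumab baseline is Week 16; if those patients are included, their times carry about 16 placebo-only weeks

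*SAP*

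**What the plan says.** SAP 6.11.8.2.1 covers evaluable patients in the Safety Population "for Blinded Treatment Dosing Period (Period 2), and Combined Blinded Treatment Dosing and Extended Treatment Periods (Combined Periods 2 and 3"). It gives a single formula for time to development of TE-ADA or NAb, in weeks: date of development, minus "Date of first injection of study treatment + 1", divided by 7. Patients without an event are censored at their last immunogenicity assessment. Quartiles with confidence intervals and a Kaplan-Meier plot follow by treatment group, if there are enough data.

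The same section says: "Baseline definition for immunogenicity analyses for the Combined Treatment Period is the same as" Table RHCH.6.9. That table gives Week 0 for patients on ixekizumab throughout and Week 16 for those who move from placebo. The text above the table (SAP 6.11.8.1.3) says that for patients not randomized to ixekizumab "baseline is the last non-missing observation on, or prior to, the date of the first injection of ixekizumab".

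On the term itself, SAP 6.1.1 states "Period 2 starts at the first injection of study treatment at Week 0 (Visit 2"), for both arms. Protocol 8.1 equates the two terms: "discontinuation from study treatment (investigational product"). Protocol Appendix 1 defines investigational product so that it includes placebo.

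**The concern.** In the combined analysis the clock and the baseline start on different days for placebo/ixekizumab patients. Treatment emergence is judged against Week 16, when ixekizumab is first given to them (Protocol 7.1), so no earlier sample can be an event. The formula nevertheless counts from the Week 0 placebo injection. If these patients are in the analysis, their Kaplan-Meier curve is flat to about Week 16 by construction, and any percentiles are measured from first placebo. Shown beside the ixekizumab/ixekizumab group, this would look like later antibody onset, and part of that difference would come only from the choice of origin.

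**Working it through.** The documents give no figure for time to ADA, so there is none to reproduce. The check is date arithmetic on nominal study days.

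**Inputs**
- Formula: (event date − origin date + 1) / 7 (SAP 6.11.8.2.1).
- Origin as written: day 0, first study-treatment injection (SAP 6.1.1).
- First ixekizumab in the placebo arm: Week 16, day 112, window ±4 days (Protocol 7.1 and Section 2).
- Scheduled Period 3 immunogenicity samples: Week 24 (day 168), Week 36 (day 252), Week 52 (day 364), plus the early termination visit (Protocol Section 2).
- Period 2 samples after baseline: Weeks 1, 2, 4, 8, 12 and 16 (Protocol Section 2).
- Size of the placebo arm: about 140 randomized 1:1, so 140/2 = 70 (Protocol 10.1).

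**Offset**
112/7 = 16.0 weeks. With the visit window: 108/7 = 15.4 to 116/7 = 16.6 weeks.

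**Recorded time for a placebo/ixekizumab patient, in weeks**

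| First positive sample | As written | From first ixekizumab | Difference |
|---|---|---|---|
| Week 24 | (168 − 0 + 1)/7 = 24.14 | (168 − 112 + 1)/7 = 8.14 | 16.0 |
| Week 36 | 253/7 = 36.14 | 141/7 = 20.14 | 16.0 |
| Week 52 | 365/7 = 52.14 | 253/7 = 36.14 | 16.0 |

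Censoring times shift by the same amount. Times for ixekizumab/ixekizumab patients do not change, because their first study treatment is ixekizumab. The Period 2 analysis does not change either, since its clock and baseline are both Week 0.

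**Illustration of the effect on the curves**
The documents give no expected incidence. Assume the same constant on-drug hazard in both groups, with a proportion p positive by 36 weeks on drug. Then h = −ln(1 − p)/36. At Week 24 on the written clock, cumulative incidence is 1 − exp(−24h) for ixekizumab/ixekizumab and 1 − exp(−(24 − 16)h) = 1 − exp(−8h) for placebo/ixekizumab.

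| p (assumed) | Ixekizumab/ixekizumab | Placebo/ixekizumab, as written |
|---|---|---|
| 5% | 3.4% | 1.1% |
| 10% | 6.8% | 2.3% |
| 20% | 13.8% | 4.8% |

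The two groups are identical on drug by assumption, so the whole gap comes from the origin. At p of 5% or 10% the ixekizumab/ixekizumab curve reaches only 7.1% or 14.1% by Week 52. The 25th percentile would then not be reached, and the distortion would show mainly in the plot.

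**The case against.** The strongest objection is that placebo/ixekizumab patients may not be in this analysis. SAP 6.1.3 describes selected combined-period safety analyses in the Safety Population randomized to ixekizumab, and one row of Table RHCH.6.2 lists that restricted set with a single treatment group. On that reading first study treatment is first ixekizumab and the offset is zero. This stands as a real ambiguity. Inclusion is still the better reading. SAP 6.11.8.2.1 names the Safety Population without the restriction, and SAP 6.1.5 defines it as all randomized and dosed patients. The section also adopts a baseline table whose second row is for placebo patients and would otherwise do nothing there. By-treatment-group reporting points the same way, though less firmly, because it also serves Period 2.

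A second objection is that a Week 16 origin was intended. SAP 6.1.2 uses the term study treatment for the Week 16 injection that opens Period 3, and the footnote to Table RHCH.6.9 reads "Last non-missing observation on, or prior to, the date of the first injection of study treatment at the defined week". But both uses name the week and the formula does not. SAP 6.11.8.1.3 also uses first injection of ixekizumab as a separate term. A programmer following the formula would code Week 0.

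Third, correcting the origin will not make the groups comparable. On schedule, placebo/ixekizumab patients are first sampled about 8 weeks after first ixekizumab, against Week 1 in the ixekizumab arm, so detection is later by design. This stands in full.

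**Conclusion.** The mismatch between clock and baseline is in the text and should be corrected. Its size is 16 weeks nominally (15.4 to 16.6) in every event and censoring time of the affected patients. That size depends on placebo/ixekizumab patients being included and on the formula being coded as written.

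A reader might infer more than the documents support:
- **That the whole placebo arm is affected.** About 70 is a ceiling. Only evaluable patients who reach Week 16 and receive ixekizumab contribute.
- **That a positive result 4 weeks after first ixekizumab would be recorded at 20 weeks.** No sample is scheduled at Week 20, so this would need an early termination or unscheduled sample. The scheduled case is 8 against 24.
- **That all of any apparent delay in onset comes from the origin.** Sparser sampling after the switch contributes as well.
- **That immunogenicity conclusions in general are wrong.** TE-ADA classification, incidence and titre do not use this formula. The affected outputs are descriptive and produced only if data suffice, and Table RHCH.6.2 plans no between-group test for the combined periods. No primary or alpha-controlled result changes.

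**What to change.** In SAP 6.11.8.2.1:
1. For Combined Periods 2 and 3, count from the date of first injection of ixekizumab, matching Table RHCH.6.9. Keep the first study-treatment injection for Period 2.
2. State which population enters the combined analysis and whether it includes placebo/ixekizumab patients. If it does, say that placebo patients who never receive ixekizumab are left out, since they would have no time origin.
3. Add a note to the Kaplan-Meier output that the sampling schedules after first ixekizumab differ (first scheduled sample at about 8 weeks against Week 1), so onset times should not be read as directly comparable between groups.

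The cost is a few sentences in the SAP and one line of code for the origin date. No new data are needed.

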6.11.8.2.2. Analyses of ADA Effects on Efficacy

Efficacy analyses for Period 2 and Period 3 will be conducted on all evaluable patients within the ITT Population and Extended Treatment Period Population.

The ASAS40, ASAS20, ASDAS inactive disease and ASDAS < 2.1 at week 16 with NRI will be summarized by the TE-ADA status groups as described in Section 6.11.8.2.

A logistic regression model with treatment group, TE-ADA status group (excluding patients in the TE-ADA inconclusive category for TE-ADA, excluding TE-ADA positive and co-occurring NAb inconclusive subgroups for NAb), and the interaction of treatment group-by-TE-ADA status group included as factors will be used to test the interaction of treatment group-by-TE-ADA status group for ITT Population during Period 2. The p-value associated with the interaction term will be used to assess if the treatment groups effect is consistent across the TE-ADA status group. When the interaction term is statistically significant, the association between responder status and treatment depends, in some manner, on the TE-ADA status group. The interaction will be tested at the 10% significance level. Treatment differences will be evaluated within each subgroup using Fisher's exact test regardless of whether the interaction is statistically significant.

Response rates for ASAS40, ASAS20, ASDAS inactive disease and ASDAS < 2.1 at Week 16 will be provided and compared among the TE-ADA status (and TE-ADA tiers) and NAb status groups for the ITT Population who were treated with ixekizumab.

Descriptive statistics for ASAS40 and ASAS20 at Week 52 based on the TE-ADA status (and TE-ADA tiers) and NAb status group will be provided for the Extended Treatment Period Population. No inferential statistics will be performed.

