10.1. Sample Size Determination

Approximately 140 patients will be randomized at a 1:1 ratio in the Blinded Treatment Dosing Period (Period 2) to ixekizumab 80 mg Q4W with a starting dose 160 mg and placebo.

For 90% power to test the superiority of ixekizumab Q4W to placebo for ASAS40 at Week 16 in bDMARD-naïve patients, at least 61 bDMARD-naïve patients per treatment group would be needed. The following assumptions were used for the power calculations for ASAS40 response rates: 44% for ixekizumab 80 mg Q4W treatment group and 16% for the placebo group in bDMARD naïve patients.

For the key secondary efficacy endpoint ASAS40 response at Week 16 compared to placebo group in overall study population, the power would be >90%. The assumptions are 42% response rate for ixekizumab 80 mg Q4W treatment group and 15% for the placebo group in overall study population.

These assumptions are based on the review of historical clinical studies in r-axSpA (etanercept, adalimumab, infliximab, certolizumab, and golimumab [Davis et al. 2003; van der Heijde et al. 2005, 2006; Inman et al. 2008, Landewé et al. 2014]) and recent secukinumab trials including both TNF inhibitor experienced patients and naïve patients (Baeten et al. 2014b; Sieper et al. 2014).

A 2-sided Fisher's exact test at the 0.05 level is assumed. Sample size and power estimates were obtained from nQuery® Advisor 7.0.

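### The Period 2 treatment-by-TE-ADA interaction and within-status placebo tests split patients by a post-randomisation status driven mainly by ixekizumab, so a non-significant result cannot support a consistent effect

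*SAP*

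**What the plan says.** SAP 6.11.8.2.2 summarises four Week 16 endpoints by antibody status: ASAS40, ASAS20, ASDAS inactive disease and ASDAS below 2.1. A logistic model with treatment, status group and their product "will be used to test the interaction of treatment group-by-TE-ADA status group for ITT Population during Period 2". The level is given: "The interaction will be tested at the 10% significance level". The use of the result is given too: "The p-value associated with the interaction term will be used to assess if the treatment groups effect is consistent across the TE-ADA status group". TE-ADA-inconclusive patients are left out of the TE-ADA model, and TE-ADA-positive patients with inconclusive NAb are left out of the NAb version. Fisher's exact test then compares the arms within each status, whatever the interaction shows.

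Other sections bear on this:
- SAP 6.11.8.1.3 defines TE-ADA positivity by a titre rise over baseline, and the inconclusive class by drug levels that may interfere with the assay.
- SAP 6.11.8.2 defines NAb status and titre groups among TE-ADA-positive patients only.
- Protocol 7.1 gives placebo patients their first ixekizumab at Week 16, where Period 2 ends.
- SAP 6.12.1 makes a baseline subgroup category holding under 10% of the population descriptive only. SAP 6.11.8.2.2 has no such rule.
- SAP 6.1.1 substitutes Fisher's exact test when sparse data defeat the logistic model.
- SAP 6.11.8.2.2 also compares response across TE-ADA, titre and NAb groups among ixekizumab-treated patients, and gives Week 52 results descriptively.

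**The concern.** A treatment-by-subgroup interaction is interpretable when the subgroup is fixed before randomisation and both arms populate each level. Neither condition is secure here. Antibody status arises after randomisation and mainly through exposure to the drug under test, and during Period 2 the placebo arm has no such exposure. The interaction needs an ixekizumab-versus-placebo odds ratio among TE-ADA-positive patients, and there may be no placebo patients to supply one.

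Two things are at stake. The interaction p-value is likely to be absent or non-significant whatever antibodies do, and the SAP's wording invites a non-significant value to be read as a consistent effect. Also, the TE-ADA-negative comparison sets an ixekizumab arm that has lost its positive and inconclusive patients against a placebo arm that has lost almost none.

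**Working it through.** **Inputs from the documents.** Allocation: "Approximately 140 patients will be randomized at a 1:1 ratio in the Blinded Treatment Dosing Period (Period 2"), so about 70 per arm. Response: "42% response rate for ixekizumab 80 mg Q4W treatment group and 15% for the placebo group in overall study population". Interaction level: 0.10. SAP 6.11.8.2.2 gives no level for the within-status tests; 0.05 is used here. The documents give no TE-ADA rate for either arm, so those rates are assumed and varied.

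**The plan's own figure.** There is none for the antibody analyses. The sample size does reproduce. Protocol 10.1 says "at least 61 bDMARD-naïve patients per treatment group would be needed" for 90% power at "44% for ixekizumab 80 mg Q4W treatment group and 16% for the placebo group in bDMARD naïve patients", and "A 2-sided Fisher's exact test at the 0.05 level is assumed". Exact enumeration gives 90.5% at 61 per arm (89.9% at 60). For 42% against 15% with 70 per arm it gives 93.2%, in line with the stated power above 90%. The sample size is not in dispute.

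**Placebo TE-ADA-positive cell.** Let q be the placebo TE-ADA rate. The expected count is 70q and P(empty) = (1 − q)^70. A finite interaction odds ratio needs at least one responder and one nonresponder in this cell. With 15% response:

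P(both present) = 1 − (1 − 0.85q)^70 − (1 − 0.15q)^70 + (1 − q)^70.

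For q = 0.02 this is 1 − 0.301 − 0.810 + 0.243 = 0.132.

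| Assumed q | Expected positives | P(empty) | P(at most one) | P(both present) |
|---|---|---|---|---|
| 0% | 0 | 1.00 | 1.00 | 0 |
| 0.5% | 0.35 | 0.70 | 0.95 | 0.013 |
| 1% | 0.7 | 0.49 | 0.84 | 0.044 |
| 2% | 1.4 | 0.24 | 0.59 | 0.13 |
| 3% | 2.1 | 0.12 | 0.38 | 0.23 |
| 5% | 3.5 | 0.03 | 0.13 | 0.39 |

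The last column is necessary, not sufficient: the other response cells must be non-empty as well.

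**Power of the interaction test.** Suppose antibodies remove the whole benefit, so that response in TE-ADA-positive ixekizumab patients falls from 42% to 15%. The saturated model was simulated with a Wald test at 0.10, 200,000 trials per scenario and ixekizumab TE-ADA rates of 5-20%. Rejection occurs in 0% of trials at q = 0, 0.3-2.5% at 1%, 0.7-6.9% at 2% and 1.1-10.9% at 3%. Most of these are below the nominal 10%.

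**Fisher's test among positives.** With k ixekizumab and m placebo positives, the smallest attainable p is 1/C(k + m, m). For m = 1 this is 1/(k + 1): 0.125 at k = 7, 0.067 at k = 14, and 0.05 only at k = 19. Power for 42% against 15% is at most 0.4% over ixekizumab rates of 5-20% and placebo rates of 0-2%.

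**Selection in the TE-ADA-negative comparison.** As an illustration, assume antibodies are inert. Half the patients have poor prognosis (24% response on ixekizumab) and half good (60%). TE-ADA occurs in 15% of the poor and 5% of the good ixekizumab patients, and in no placebo patient.
- Positive share: 0.5 × 0.15 + 0.5 × 0.05 = 0.10.
- Response in positives: (0.075 × 0.24 + 0.025 × 0.60)/0.10 = 33%.
- Response in negatives: (0.425 × 0.24 + 0.475 × 0.60)/0.90 = 43%.

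The negative contrast is 43 − 15 = 28 points against a true 27. Antibodies do nothing here, yet response differs by 10 points between positive and negative ixekizumab patients.

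**Safeguards.** Fisher's exact test compares arms and does not test an interaction, so the 6.1.1 fallback does not answer the question. Ten percent of 140 is 14 patients. Assumed rates of 18% on ixekizumab and 1% on placebo give 12.6 + 0.7 = 13.3 positives, so the 6.12.1 rule would bar testing even then, but it is not carried into this section.

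**The case against.** The placebo rate is assumed. The SAP recognises pre-existing antibody, a placebo patient can qualify through a titre rise, and placebo patients are sampled at each Period 2 visit. At 5% the cell would seldom be empty. This stands: a reader might infer that placebo patients cannot be TE-ADA positive or that the model is bound to fail, and the documents do not establish either.

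The SAP's wording after the interaction test is associational; it does not claim to show that antibodies cause loss of efficacy. That is fair. The consistency sentence nevertheless gives the p-value an interpretation it cannot carry at low placebo rates.

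A reader might also infer that the TE-ADA-negative contrast is seriously biased. The documents do not support that, and the illustration moves it by one point. What can be said is that the comparison is no longer randomised.

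Finally, the objective is exploratory, Protocol 10.3.11 asks for evaluation as appropriate, and the ixekizumab-only comparison is already planned. All true, and this limits the consequence. That comparison is itself post-treatment and weak. In the scenario where antibodies remove the whole benefit, it rejects at 0.10 in about 0.5%, 9%, 28% and 46% of trials for ixekizumab TE-ADA rates of 5%, 10%, 15% and 20%. It avoids the empty placebo cell but does not identify an antibody effect.

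**Conclusion.** The point holds for the two procedures that use placebo as comparator within antibody status. Their dependence on a post-randomisation, mainly drug-driven status follows from the documents' own definitions and dosing schedule. The size depends on the unknown placebo rate. At 0.5-2% the placebo-positive cell is empty with probability 0.70-0.24, and a finite interaction estimate is possible in at most about 1-13% of trials. At 5% emptiness is rare (0.03), but the necessary condition for a finite estimate is met only 39% of the time. The NAb version is sparser, since it subdivides the positives.

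At low placebo rates, a non-significant interaction is therefore close to uninformative and should not be reported as a consistent effect. It would be wrong to extend this to the trial's main results: these analyses lie outside the primary and major secondary tests, whose conclusions are unaffected.

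**What to change.** In SAP 6.11.8.2.2, remove the interaction p-value and the within-status Fisher tests against placebo, or make them descriptive only. Delete the sentence that uses the p-value to assess consistency. Report the planned ixekizumab-only response rates by TE-ADA status, titre and NAb with confidence intervals, labelled as non-randomised association, and show inconclusive patients as their own group.

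No new data are needed. The cost is that exploratory p-values for four endpoints are no longer reported. The ixekizumab-only comparison remains imprecise, which the intervals will show.
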